10.1.8 Protocol adherence and protocol amendments

This protocol defines the study objectives, the study procedures and the data to be collected on study participants. Additional assessments required to ensure safety of participants should be administered as deemed necessary on a case by case basis. Under no circumstances including incidental collection is an Investigator allowed to collect additional data or conduct any additional procedures for any purpose involving any investigational drugs under the protocol, other than the purpose of the study. If despite this interdiction prohibition, data, information, observation would be incidentally collected, the Investigator shall immediately disclose it to Novartis and not use it for any purpose other than the study, except for the appropriate monitoring on study participants.

Investigators ascertain they will apply due diligence to avoid protocol deviations. If an Investigator feels a protocol deviation would improve the conduct of the study this must be considered a protocol amendment, and unless such an amendment is agreed upon by Novartis and approved by the IRB/IEC and health authorities, where required, it cannot be implemented.

10.1.8.1 Protocol amendments

Any change or addition to the protocol can only be made in a written protocol amendment that must be approved by Novartis, health authorities where required, and the IRB/IEC prior to implementation.

Only amendments that are required for participant safety may be implemented immediately provided the health authorities are subsequently notified by protocol amendment and the reviewing IRB/IEC is notified.

Notwithstanding the need for approval of formal protocol amendments, the Investigator is expected to take any immediate action required for the safety of any participant included in this study, even if this action represents a deviation from the protocol. In such cases, Novartis should be notified of this action and the IRB/IEC at the study site should be informed according to local regulations.

10.2 Appendix 2: Abbreviations and definitions

10.2.1 List of abbreviations

ACEI Angiotensin Converting Enzyme (inhibitor)

AE Adverse Event

AHA American Heart Association

AKI Acute Kidney Injury

ARB Angiotensin Receptor Blocker

ARNI Angiotensin Receptor Neprilysin Inhibitor

AT1 Angiotensin II Type 1

ATC Anatomical Therapeutic Classification

bid bis in die/twice a day
BMI Body Mass Index
BP Blood Pressure
BUN Blood Urea Nitrogen
CCB Calcium Channel Blocker

CHBP Child Bearing Potential Females

CIOMS Council for International Organizations of Medical Sciences

COX Cyclo-oxygenase Cr Creatinine

CRA Clinical Research Associate

CRF Case Report/Record Form (paper or electronic)

CSR Clinical Study Report
CV Cardiovascular

DAR Dosage Administration Record
DBP Diastolic Blood Pressure

eCRF electronic Case Report/Record Form

EDC Electronic Data Capture

eGFR Estimated Glomerular Filtration Rate

EMA European Medicines Agency

ENR Enrolled Set EoS End of Study

eSAE Electronic Serious Adverse Event

eSource Electronic Source

FSH Follicle Stimulating Hormone GCP Good Clinical Practice

HF Heart Failure

IUS

HFrEF HF with Reduced Ejection Fraction

IB Investigator's Brochure ICF Informed Consent Form

ICH International Council for Harmonization of Technical Requirements for

Intrauterine System

Registration of Pharmaceuticals for Human Use

IEC Independent Ethics Committee

INInvestigator NotificationIRBInstitutional Review BoardIUDIntrauterine Device

KDIGO	Kidney Disease: Improving Global Outcomes	
LLN	Lower Limit of Normal	
MedDRA	Medical Dictionary for Regulatory Activities	
MRP2	Multidrug resistance protein 2	
NEP	Neprilysin	
NSAID	Non-steroidal Anti-Inflammatory Drug	
PALS	Pediatric Advanced Life Support	
PCR	Protein-Creatinine Ratio	
PK	Pharmacokinetic(s)	
PS	Patient Safety	
PV	Pharmacovigilance	
OLE	Open Label Extension	
RAAS	Renin-Angiotensin-Aldosterone System	
RMP	Risk Management Plan	
RRR	Relative Risk Reduction	
SAE	Serious Adverse Event	
SAF	Safety Set	
SAP	Statistical Analysis Plan	
SBP	Systolic Blood Pressure	
SGOT	Serum Glutamic Oxaloacetic Transaminase	
SGPT	Serum Glutamic Pyruvic Transaminase	
SoA	Schedule of Activities	
SUSAR	Suspected Unexpected Serious Adverse Reaction	
TEAE	Treatment- Emergent Adverse Event	
ULN	Upper Limit of Normal	
UNS	Unscheduled	
WHO	World Health Organization	

10.2.2 Definitions

Additional treatment	Medicinal products that may be used during the clinical trial as described in the protocol, but not as an investigational medicinal product (e.g. any background therapy)	
Assessment	A procedure used to generate data required by the study	
Biologic Samples	A biological specimen including, for example, blood (plasma, serum), saliva, tissue, urine, stool, etc. taken from a study participant	
Cohort	A group of individuals who share a common exposure, experience or characteristic, or a group of individuals followed-up or traced over time	
Discontinuation from study	Point/time when the participant permanently stops receiving the study treatment and further protocol required assessments or follow-up, for any reason. No specific request is made to stop the use of their samples or data.	
Discontinuation from study treatment	Point/time when the participant permanently stops receiving the study treatment for any reason (prior to the planned completion of study intervention administration, if any). Participant agrees to the other protocol required assessments including follow-up. No specific request is made to stop the use of their samples or data.	

Dosage	Dose of the study treatment given to the participant in a time unit (e.g. 100 mg	
	once a day, 75 mg twice a day)	
Electronic Data Capture (EDC)	Electronic data capture (EDC) is the electronic acquisition of clinical study data using data collection systems, such as Web-based applications, interactive voice response systems and clinical laboratory interfaces. EDC includes the use of Electronic Case Report Forms (eCRFs) which are used to capture data transcribed from source data/documents used at the point of care	
End of the clinical trial	The end of the clinical trial is defined as the last visit of the last participant.	
Enrollment	Point/time of participant entry into the study at which informed consent must be obtained. The action of enrolling one or more participants	
Investigational drug/ treatment	The drug whose properties are being tested in the study	
Medication number	A unique identifier on the label of medication kits	
Other treatment	Treatment that may be needed/allowed during the conduct of the study (i.e. concomitant or rescue therapy)	
Part	A sub-division of a study used to evaluate specific objectives or contain different populations. For example, one study could contain a single dose part and a multiple dose part, or a part in participants with established disease and in those with newly-diagnosed disease	
Participant	A trial participant (can be a healthy volunteer or a patient). "Participant" terminology is used in the protocol whereas term "Subject" is used in data collection	
Participant number	A unique number assigned to each participant upon signing the informed consent. This number is the definitive, unique identifier for the participant and should be used to identify the participant throughout the study for all data collected, sample labels, etc.	
Period	The subdivisions of the trial design (e.g. Screening, Treatment, Follow-up) which are described in the Protocol. Periods define the study phases and will be used in clinical trial database setup and eventually in analysis	
Personal data	Participant information collected by the Investigator that is coded and transferred to Novartis for the purpose of the clinical trial. This data includes participant identifier information, study information and biological samples.	
Screen Failure	A participant who did not meet one or more criteria that were required for participation in the study	
Source Data/Document	Source data refers to the initial record, document, or primary location from where data comes. The data source can be a database, a dataset, a spreadsheet or even hard-coded data, such as paper or eSource	
Start of the clinical trial	The start of the clinical trial is defined as the signature of the informed consent by the first participant	
Study treatment	Any drug or combination of drugs or intervention administered to the study participants as part of the required study procedures; includes investigational drug(s), control(s) or background therapy	
Treatment arm/group	A treatment arm/group defines the dose and regimen or the combination, and may consist of 1 or more cohorts.	
Variable (or endpoint)	The variable (or endpoint) to be obtained for each participant that is required to address the clinical question. The specification of the variable might include whether the participant experiences an intercurrent event.	

Withdrawal of consent	Withdrawal of consent from the study occurs when the participant explicitly requests to stop use of their data and/or biological samples AND no longer wishes to receive study treatment, AND does not agree to further protocol required assessments. This request should be in writing (depending on local regulations) and recorded in the source documentation.
	This request should be distinguished from a request to discontinue the study. Other study participant's privacy rights are described in the corresponding informed consent form.

10.3 Appendix 3: Clinical laboratory tests

10.3.1 Clinically notable laboratory values and vital signs

Table 10-1 Clinically notable laboratory values

Parameter	Conventional	SI Alert	SI
	Units	Value	Units
Hematology			
Red Blood Cell Count	x10E6/uL	>50% increase and > Upper limit of normal (ULN);	x10E12/L
		>30% decrease and < Lower limit of normal (LLN).	
Hemoglobin	g/dL	>50% increase and >ULN;	g/L
		(>30% decrease and <lln) <70.<="" any="" or="" td="" value="">	</lln)>	
Hematocrit	%	>50% increase and >ULN;	L/L
		>30% decrease and <lln.< td="">	</lln.<>	
White Blood Cell	x10E3/uL	>50% increase and >ULN;	x10E9/L
Count		>50% decrease and <lln.< td="">	</lln.<>	
Platelet Count	x10E3/uL	>75% increase and >ULN;	x10E9/L
		>50% decrease and <lln.< td="">	</lln.<>	
Chemistry			
BUN	mg/dL	>50% increase and >ULN	mmol/L
Creatinine	mg/dL	>50% increase and >ULN	umol/L
Albumin	g/dL	<20	g/L
Glucose	mg/dL	>50% increase and >ULN;	mmol/L
	· ·	(>50% decrease and <lln) <3.3.<="" any="" or="" td="" value="">	</lln)>	
Total Bilirubin	mg/dL	>100% increase and >ULN	umol/L
AST (SGOT)	U/L	>150% increase and >ULN	U/L
ALT (SGPT)	U/L	>150% increase and >ULN	U/L
Sodium	mEq/L	(>5% increase and >ULN) or any value >150;	mmol/L
		(>5% decrease and <lln) <125<="" any="" or="" td="" value="">	</lln)>	
Potassium	mEq/L	(>20% increase and >ULN) or any value >6;	mmol/L
	7	(>20% decrease and <lln) <3.<="" any="" or="" td="" value="">	</lln)>	
Chloride	mEq/L	>10% increase and >ULN;	mmol/L
	,	>10% decrease and <lln< td="">	</lln<>	
Calcium	mg/dL	>10% increase and >ULN;	mmol/L
	J	>10% decrease and <lln.< td="">	</lln.<>	
Uric Acid	mg/dL	>50% increase and >ULN	mmol/L

Increase and decrease are defined as compared to the baseline value of PANORAMA-HF OLE study (i.e. Visit 500).

Table 10-2 Criteria for clinically notable vital signs

Age	HR [min ⁻¹]	SBP [mmHg]	DBP [mmHg]	RR [min ⁻¹]
1-3 years	<60, >120	<76, >115	<45, >75	<14, >35
3-6 years	<55, >120	<82, >120	<50, >80	<12, >30

Novartis Confidential Page 54 of 66 Clinical Trial Protocol (Version No. v00) Protocol No. CLCZ696B2319E2

Age	HR [min ⁻¹]	SBP [mmHg]	DBP [mmHg]	RR [min ⁻¹]
6-12 years	<50, >105	<90, >130	<50, >80	<10, >27
>12 years	<45, >95	<90, >145	<55, >90	<8, >23

The following participant engagement initiative is included in this study and will be provided, as available for distribution to study participants at the time points indicated. If compliance is impacted by cultural norms or local laws and regulations, sites may discuss modifications to these requirements with Novartis.

• Plain language trial summary - after clinical study report (CSR) publication

10.5 Appendix 5: Renal safety monitoring

10.5.1 Specific Renal Alert Criteria and Actions and Event Follow-up

Table 10-3 Specific renal alert criteria and actions

Renal Event	Actions
eGFR decrease 25 – 49%	Consider causes and possible interventions
	 Repeat laboratory values within 48 hrs of receipt of abnormal test results. Assess patient for signs and symptoms of illness, acute kidney injury (AKI), etc.
eGFR decrease ≥ 50% *	Consider causes and possible interventions
OR if <18 years old, eGFR <	Repeat assessment within 24-48h if possible
35 mL/min/1.73 m ²	 Repeat laboratory values within 48 hrs of receipt of abnormal test results. Assess patient for signs and symptoms of illness, AKI, etc.
	 Consider drug interruption or discontinuation unless other causes are diagnosed and corrected
	Consider referral to nephrologist for diagnosis and management
	Consider patient hospitalization and specialized treatment
New onset dipstick proteinuria ≥ 3+	 Confirm presence of true proteinuria by quantification: protein:creatinine on first morning void
OR	Consider causes and possible interventions
Protein-creatinine ratio (PCR)	Assess serum albumin & serum total protein
≥ 1g/g creatinine (Cr)	Repeat assessment to confirm
	 Consider drug interruption or discontinuation unless other causes are diagnosed and corrected
	Consider referral to a nephrologist
New onset hematuria ≥ 3+ on urine dipstick	 Obtain urine microscopy to distinguish hemoglobinuria or myoglobinuria from hematuria
	Assess serum Cr
	 Exclude infection, trauma, calculi, bleeding from the distal urinary tract/bladder, menstruation
	Consider bleeding disorder

^{*} Corresponds to KDIGO criteria for Acute Kidney Injury

eGFR is calculated using a modified Schwartz formula for participants <18 years:

eGFR (ml/min/1.73m²) = 0.413 x height (cm) / serum creatinine (mg/dl). The most recently available height should be used for calculation.

eGFR decrease are defined as compared to the baseline value of PANORAMA-HF OLE study (i.e. Visit 500).

Urine samples for testing for renal monitoring, and particularly those for the PCR ratio determination, must be collected at the first morning void.

Table 10-4 GFR by age for up-titration

age (mL/min/1.73m ²)**	age (mL/min/1.73m ²)
≥ 31	< 31
≥ 38	< 38
≥ 30	< 30
2	≥ 31 ≥ 38

^{*} Age rounded to nearest whole number ** up-titration criteria

Source: (Peters, Gordon 1999)

10.6 **Appendix 6: Guidelines for the management of renal dysfunction**

General principles:

Glomerular filtration rate in HF patients depends on intrinsic renal function and on a balance between afferent and efferent glomerular arterial tonicity. This tonicity is partly regulated by a stimulation of angiotensin II and could be affected by either study medication. Moreover, renal dysfunction may develop or may deteriorate in some patients after study drug administration. These recommendations have been developed to guide the investigators in managing patients with renal dysfunction after enrollment and the first dose of sacubitril/valsartan.

Two types of response to serum creatinine increase are described:

Surveillance situation

If, at any time after enrollment and the first open-label dose of sacubitril/valsartan, eGFR%* decreases by $\geq 50\%$ from baseline in PANORAMA-HF OLE study (i.e. Visit 500), the investigator will check for potentially reversible causes of renal dysfunction such as:

- non-steroidal anti-inflammatory drug intake, antibiotics, or other treatments known to cause creatininemia
- volume decrease, including that resulting from excessive dosing of diuretics
- urinary infection
- urinary tract obstruction
- study medication

Action situation

If a patient eGFR* decreases by ≥ 50% from baseline of PANORAMA-HF OLE study (i.e. Visit 500) (or if serum creatinine concentration rises above 3 mg/dL (265 µmol/L), the investigator will check for potentially reversible causes of renal dysfunction (see above). If the investigator judges that study medication has to be stopped, he/she will have to contact the Novartis medical monitor or his/her designee. Thereafter, serum creatinine assessments will have to be repeated at least each week until levels return to acceptable values. If study medication was stopped, every effort will be done to restart it again, according to clinical conditions.

*eGFR is calculated using a modified Schwartz formula for participants <18 years.

For participants ≥18 years, an adult formula for eGFR will be utilized (Reference: Novartis Nephrology Guidance document)

10.7 Appendix 7: American heart association (AHA) pediatric advanced life support (PALS) guidelines

Table 10-5 5th percentile systolic blood pressure (SBP) table

Age	SBP percentile	SBP (mmHg)
1 month to < 1 year	5 th	70
1 year	5 th	72
2 years	5 th	74
3 years	5 th	76
4 years	5 th	78
5 years	5 th	80
6 years	5 th	82
7 years	5 th	84
8 years	5 th	86
9 years	5 th	88
10 years	5 th	90
11 years	5 th	90
12 years	5 th	90
13 years	5 th	90
14 years	5 th	90
15 years	5 th	90
16 years	5 th	90
17 years	5 th	90

^{*} AHA PALS guidelines 2010 (Kleinman et al 2010) are widely used criteria for hypotension in acute HF patients. The formula (for 1 year and older: 70 mmHg + 2 x Age, up to age 10) is understood to provide the 5th SBP percentile up to 10 years. For children 1 month to < 1 year and ≥ 10 years, the AHA PALS guidelines 2010 5th percentile is set at 70 mmHg and 90 mmHg respectively. NOTE:

This formula approximates the population-based 5th percentile BP data; however, the margin of error increases with increasing age, with the PALS formula value generally providing a lower value.

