4.1 Overall design

This trial (CLCZ696B2319E2) is a multicenter, open-label extension study for Japanese patients who have successfully completed the PANORAMA-HF OLE study (Refer to Section 1.2 Schema for study design figure). PANORAMA-HF OLE study is an on-going Phase 3b study in pediatric patients with systemic left ventricular systolic dysfunction to evaluate long- term safety and tolerability of sacubitril/valsartan in eligible PANORAMA-HF participants.

Only Japanese patients who successfully completed PANORAMA-HF OLE study and fulfill protocol requirements (see Section 5) are eligible to participate in this study, and will be offered the option to initiate treatment with sacubitril/valsartan by enrolling into this study at the discretion of the Investigator. Participants who permanently discontinued study drug treatment during PANORAMA-HF OLE study are not eligible for this study (see Section 5.2).

For all consenting patients eligibility for this study will be assessed at the first visit (Visit Day1) and the study medication will be initiated (see Section 8 for details). The first visit (Visit Day1) is the same day as the End of Study visit (Visit 599) of PANORAMA-HF OLE study. Participants who turned 18 years old during PANORAMA-HF OLE study, and who qualify, are eligible to participate in this study.

The starting dose of study drug will be determined by the Investigator considering the participant's condition The dose level at the end of study visit of PANORAMA-HF OLE study may remain the same, or the dose level may be changed at the discretion of the Investigator.

All participants have a target dose (dose level 4) of 3.1 mg/kg bid. If a participant is unable to tolerate up-titration to a higher sacubitril/valsartan dose level or at the discretion of the Investigator, participants may be maintained on lower dose levels of sacubitril/valsartan (dose level 1-3, see Table 4-1). Please see Section 6.4.1 for dose adjustments. In case of a consecutive 3-month interruption of study treatment, participant should be discontinued from the study and should complete the End of Study visit (Visit EOS).

Table 4-1 Study drug dose levels for sacubitril/valsartan

Dose levels for pediatric formulation				
Dose level 1	0.8 mg/kg bid.			
Dose level 2	1.6 mg/kg bid.			
Dose level 3	2.3 mg/kg bid.			
Dose level 4	3.1 mg/kg bid.			
Dose levels for adult formulation				
Dose level 1	50 mg bid.			
Dose level 2	100 mg bid.			
Dose level 3	150 mg bid.			

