5.1 Inclusion criteria

Participants eligible for inclusion in this study must meet all of the following criteria:

- 1. Signed informed consent as well as assent at an appropriate age must be obtained prior to participation in the study.
- 2. Male or female, inpatient or outpatient, and < 18 years of age (at the time of signing informed consent).
- 3. Patients who have completed PANORAMA-HF OLE study and are able to be safely enrolled into this study as judged by the Investigator.

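### For a participant aged 18 or over, the Appendix 6 trigger of a ≥50% eGFR fall appears to compare an adult-formula value with a modified Schwartz reference (minor)

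*Protocol*

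**What the plan says.** **Trigger.** Both situations in Protocol Section 10.6 (Appendix 6), surveillance and action, use the same eGFR threshold. In the action situation eGFR "decreases by ≥ 50% from baseline of PANORAMA-HF OLE study (i.e. Visit 500"), or serum creatinine exceeds 3 mg/dL.

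**Formula in Appendix 6.** The footnote attached to eGFR sets the equation by age. Under 18 it is modified Schwartz. From 18: "For participants ≥18 years, an adult formula for eGFR will be utilized (Reference: Novartis Nephrology Guidance document"). The adult equation is not named in either document.

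**Formula in Appendix 5.** The notes to Table 10-3 (Section 10.5.1) use the same reference visit: "eGFR decrease are defined as compared to the baseline value of PANORAMA-HF OLE study (i.e. Visit 500"). They give an equation only below 18: "eGFR is calculated using a modified Schwartz formula for participants <18 years".

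**Formula elsewhere.** Table 1-2 footnote 6, Section 6.4.1, Table 6-2 and Section 8.4.4 name modified Schwartz and set no age limit. Section 8.4.4 makes it the value entered in the eCRF.

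**Age.** Inclusion criterion 2 requires "< 18 years of age (at the time of signing informed consent"). Section 4.1 nevertheless states: "Participants who turned 18 years old during PANORAMA-HF OLE study, and who qualify, are eligible to participate in this study". Treatment has no fixed end (Section 6.1.3), and Section 7.1 does not list reaching 18 as a reason to stop.

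**SAP.** Section 2.7.3 lists eGFR values and does not summarise them. Section 5.3 gives no laboratory derivations.

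**The concern.** A percent change has a clear meaning only if numerator and denominator come from the same equation. Here the denominator was fixed in childhood, while Appendix 6 changes the equation for the numerator at 18. Any systematic difference between the two equations then enters the percent fall and looks like a change in kidney function.

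Sites also have two instructions for one laboratory result at 18 or over: the adult formula in Appendix 6, and modified Schwartz in the sections on scheduled laboratory tests and dose adjustment.

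At stake is a bedside safety prompt in a study that names renal dysfunction as one of three main grounds for dose adjustment (Section 6.4.1). The absolute eGFR limit in Table 10-3 (below 35) applies only under 18. From 18, percent change is the only eGFR criterion left in that table.

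**Working it through.** The plan has no figure to reproduce. The check has two parts: which equation applies to each value, and what a mismatch does.

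**1. Equation at the reference visit.** Visit 500 is the OLE baseline and precedes consent to this study. A participant under 18 at consent was therefore under 18 at Visit 500. A participant who turned 18 during the OLE was also under 18 when it began. Under this protocol's age rule, the Visit 500 value is a modified Schwartz value. This is an inference, because the OLE protocol is not among the documents.

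**2. Equation at the current visit.** From 18, Appendix 6 requires the adult formula. Neither document says that Visit 500 is to be recalculated.

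**3. Effect of a mismatch.** Let d be the fall measured with Schwartz at both visits. Let r be the ratio of adult-formula to Schwartz eGFR on the current sample. Then:

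- apparent fall = 1 − r(1 − d)
- Schwartz fall at which the 50% trigger fires: d = 1 − 0.5/r

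The documents do not give r. The range 0.75 to 1.5 is an assumption for illustration only.

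| r (assumed) | Schwartz fall at which the trigger fires | Apparent fall when d = 50% | Apparent fall when d = 0 |
|---|---|---|---|
| 0.75 | 33.3% | 62.5% | 25% |
| 0.9 | 44.4% | 55% | 10% |
| 1.0 | 50% | 50% | 0% |
| 1.1 | 54.5% | 45% | −10% (a rise) |
| 1.25 | 60% | 37.5% | −25% (a rise) |
| 1.5 | 66.7% | 25% | −50% (a rise) |

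For example, at r = 1.25 the trigger fires at 1 − 0.5/1.25 = 60%, and a true halving reads as 1 − 1.25 × 0.5 = 37.5%. The formulas need r only on the sample in question. If r varies with creatinine, a row does not describe one patient's whole course.

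**4. Creatinine rules.** Modified Schwartz is 0.413 × height / creatinine. At constant height, creatinine when the eGFR trigger fires is 2r times its Visit 500 value: 2 × 0.75 = 1.5 up to 2 × 1.5 = 3.0. The Table 10-1 rule needs a rise above 50% and a value above the upper limit of normal. Its first part is thus met before the eGFR trigger whenever r exceeds 0.75. The 3 mg/dL limit in the action situation also does not use the formula.

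**The case against.** **The mixing is not stated.** The Appendix 6 footnote assigns the formula by participant, not by visit. It could mean the adult formula for both values once someone is 18, and the cited guidance might say so. This stands in part: mixing is the natural reading, not a certain one. The alternative is not written down, would apply an adult equation to a sample taken in childhood, and still conflicts with Section 8.4.4.

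**Sites will use Schwartz anyway.** If they follow the eCRF sections, they compare like with like. They would then be departing from Appendix 6, so the conflict remains.

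**Hardly anyone is affected.** The Section 4.1 statement conflicts with inclusion criterion 2, and SAP Table 5-1 excludes patients enrolled at 18 or over from the safety set. The clear route is turning 18 on study. The SAP defines dates only for M3 and M6 (days 91 and 183); if follow-up ended near day 183, only a participant within about six months of 18 at Day 1 would be reached. This stands as a limit on size. Exclusion from an analysis set does not, however, remove a treated patient from renal monitoring.

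**Stronger readings a reader might infer:**

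- *A true halving will be placed in the "eGFR decrease 25 – 49"% tier of Table 10-3*, which lacks the prompt "Consider drug interruption or discontinuation unless other causes are diagnosed and corrected". This needs Appendix 5 to use the adult formula from 18, which it does not say, and r above 1, which is unknown. If Appendix 5 stays on Schwartz, its tiers do not shift.
- *The trigger is insensitive at 18 or over.* The documents do not fix the direction; it may equally fire too readily.
- *Reported safety results are distorted.* The SAP only lists eGFR.

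**Conclusion.** The point holds as a minor one. For a participant treated at 18 or over, the protocol gives conflicting formulas and no rule for the Visit 500 value. On the natural reading, the Appendix 6 percent fall mixes two equations and the trigger can fire early or late for a reason unrelated to the kidney.

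This rests on two assumptions: that the Visit 500 value is a Schwartz value, and that the unavailable guidance does not settle the baseline. Size and direction cannot be determined from the documents; the 33% to 67% range only illustrates an assumed ratio.

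The consequence is limited. At most 8 patients enrol and possibly none will be 18 or over. Appendix 6 asks the investigator to look for reversible causes and leaves stopping to judgement. The creatinine rules give partial cover without using the formula, although a notable creatinine value under Table 10-1 requires only a source comment and further tests at the investigator's discretion (Section 8.4.4).

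**What to change.** Add one sentence to each of Appendices 5 and 6: every percent change in eGFR from Visit 500 uses one formula at both time points, namely modified Schwartz with current creatinine and most recent height, including after age 18. This agrees with Section 8.4.4 and does not require an adult equation to be applied to a childhood sample. Keep the adult formula only for absolute eGFR at 18 or over, and name it.

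The cost is two sentences and a second eGFR calculation for any participant aged 18 or over. No new samples and no SAP change are needed.
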